10.4.2.1.1 Comparing DS and MFC for MRD detection as an exploratory biomarker

In order to compare both approaches, DS will be performed on these samples at a molecular depth of 20,000x and at the same time the samples will also perform 10-color MFC, although researchers will be blinded to MFC results. The primary analysis will involve comparison in performance of MRD detected by DS vs. MFC patients. McNemar's Chi-squared test for paired samples (regular DS vs. MFC and ultra-deep DS vs. MFC) will be used to compare the MRD measures.

10.4.2.1.2 Analyzing circulating free DNA (cfDNA) as an exploratory biomarker

We will leverage the high sensitivity and accuracy of DS to detect and quantitate low level mutations in circulating free DNA (cfDNA) which will allow for examining the prognostic value of not only circulating tumor DNA (ctDNA) but also specific genes and mutation allele frequencies. Blood samples will be collected at baseline and pre-defined time points after treatment.

The ability to accurately assess ctDNA-based MRD would 1) allow the development and application of DS strategy for ctDNA-based longitudinal MRD monitoring in acute myeloid leukemia. While MRD is known to be a powerful tool to predict relapse, shortcomings in sensitivity and accuracy of conventional MRD techniques such as MFC limits MRD detection and risk assessment. In this regard, the unprecedented sensitivity and accuracy of DS would allow for very low-level detection of MRD and potentially more accurately predict relapse. Second, DS-based ctDNA MRD detection serves as a proof-of-principle study supporting the utility of ctDNA as a clinical biomarker of relapse in hematologic malignancies. ctDNA represents one of the most sensitive and noninvasive biomarkers in solid cancers. However, there far fewer studies exploring its utility in hematologic malignancies. Third, if shown to be an accurate predictor of relapse, ctDNA MRD detection may potentially act as a sensitive and accurate surrogate marker of long-term response in future clinical trials. Finally, ctDNA MRD detection will allow us to monitor disease progression and understand patterns of relapse in the standard and I/O with standard therapy settings, especially addressing if these are different in the setting of I/O directed therapy. Further, ctDNA monitoring can provide insights into clonal tumor hierarchy and capture subclonal dynamics.

The best cell for monitoring MRD is unclear. In chronic myeloid leukemia (CML) studies have shown that peripheral blood monitoring is comparable to bone marrow, and therefore ELN and NCCN guidelines recommend a bone marrow only at diagnosis, with interval monitoring of MRD performed on peripheral blood. Assessment of the bone marrow in the MRD state may be limited by special factors (the biopsy needle misses the residual AML), or dilution (the tube sent for MRD is usually the last one). Thus, peripheral blood may have an advantage of being a collection site for many small clusters of MRD residing in the marrow. AML derived ctDNA may be an advantage over both marrow and peripheral assessment, as it

assays discarded DNA from AML cells residing in marrow niches, but not circulating. ctDNA constitutes only a fraction of the total cfDNA pool in the plasma and, therefore, it is very likely that ctDNA occurs at very low allele frequencies. However, ctDNA is an excellent template for sensitive DNA sequencing techniques, as the ctDNA is “pre-sheared” to a uniform fragment size of ~175 bp due to Caspase activity. Not having to ultrasonically fragment the ctDNA, as opposed to normal genomic DNA, improves conversion efficiency several hundred percent. We will leverage the high sensitivity and accuracy of DS to detect and quantitate low level mutations in cfDNA which will allow for examining the prognostic value of not only ctDNA but also specific genes and mutation allele frequencies. Blood samples will be collected at baseline and pre-defined time points after treatment.

To compare cfDNA to both DS-based and MFC serial assessment for relapse prediction, separate multivariate models will be developed for each method. Relapse will be modeled as a time-to-event endpoint and Cox regression will be used to assess the association of ctDNA based MRD with this outcome. In the SWOG study, S0106 for newly diagnosed adult AML, MRD status by MFC was a strong predictor of survival, yet MRD predicted relapse-free survival with a poor c-statistic of 0.58.¹ We hypothesize that DS will lead to an improvement in prediction accuracy of relapse-risk (c-statistic 0.85). Assuming MRD-negativity (among CR/CRi) ratios of 1, 3, 0.3, and 0.45 for intensive chemo, intensive chemo + Pem, Aza + Ven, and Aza + Ven + Pem arms, respectively, and a correlation coefficient (ρ) between MFC and DS assays of 0.75 (based on MFC and NGS comparison data),²⁹ a minimum total sample size of 16, 24, 20, and 18 evaluable patients with CR/CRi would provide 80% power to detect a between-arm differencing based on a comparison of two proportional hazards survival curves with one-sided type-I error of 10% without correction for the multiplicity of endpoints: TTR; DFS; and OS.

10.4.2.2 Assessment of immune cell subsets and its correlation with the response to combine chemotherapy and anti PD-1 directed therapy

We will possibly have limited number of cells in the BM aspirate. Therefore, we will analyze the immune profile combining a high-throughput technique that will allow us to study more than 20 markers in a single cell analysis using mass cytometry (CyTOF). These techniques will provide information about the architecture of the tumor microenvironment (TME) (*i.e.*, BM) and the distribution of markers of interest detected with CyTOF. CyTOF-based single cell analysis is a new technology that combines flow cytometry with metal-conjugated antibodies detected by mass spectrometry permitting higher order multiplexing (up to 100 molecules) on a single cell analysis (Bendall *et al.*, 2011). Additionally, after fixation and permeabilization, cells will be stained with anti-human Ki-67-151Eu (B56; BD Pharmingen Ab conjugated with lanthanide MaxPar Europium Chloride 151Eu using the MaxPar X8 Ab labeling kit) for 30 min at room temperature. Cells will be acquired on CyTOF 2 instrument (DVS; Fluidigm Sciences). All data will be analyzed and graphs generated using the DVS Cytobank software (Cytobank).

We will assess these immune cell markers at different time points of therapy: At baseline (prior

to application of 7+3 chemotherapy), at the end of consolidation, after 6 months and 1 year of treatment, and at relapse. We also plan to measure CD47 levels on leukemic blasts prior to and after chemotherapy and pembrolizumab application to see whether CD47 expression levels correlate with responders *vs.* non-responders and whether expression levels change at different times of therapy. Statistical analyses of the frequency of CD8⁺, CD4⁺, Foxp3 T_{regs}, CD8⁺/Foxp3⁺ T_{regs}, T_{CM}/T_{EMRA}, T_{EM}/T_{EMRA}, the percentage of Ki67 and GzmB in PD-1⁺, Eomes⁺ CD8 T-cells to compare changes over time from baseline to several time-points will be performed by using mixed effects modeling with a Benjamini-Hochberg correction to control for false discovery rates.

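### The relapse models for flow, duplex sequencing and cfDNA have no common covariate set, internal validation or paired comparison, so their c-statistics could look better than they are, above all if read against 0.58 from another trial

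*Combined protocol and SAP*

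**What the plan says.** Section 10.4.2.1.2 sets the aim: "To compare cfDNA to both DS-based and MFC serial assessment for relapse prediction". For this, "separate multivariate models will be developed for each method", and "Relapse will be modeled as a time-to-event endpoint and Cox regression will be used". A flow model fitted in this trial is therefore part of the plan.

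The only accuracy measure named is the c-statistic. For flow in an earlier trial of newly diagnosed adult AML, the text reports that MRD status was a strong predictor of survival, "yet MRD predicted relapse-free survival with a poor c-statistic of 0.58". It continues: "We hypothesize that DS will lead to an improvement in prediction accuracy of relapse-risk (c-statistic 0.85".

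The section gives no covariate list or number, no expected count of relapses, no method for comparing c-statistics, and no split sample, cross-validation or bootstrap. Its power statement concerns a "comparison of two proportional hazards survival curves with one-sided type-I error of 10% without correction for the multiplicity of endpoints", which is a different question. Part 2 of the biomarker analysis plan in Section 10.4 adds univariate or multivariate Cox models, adjustment for prognostic factors, treatment-by-biomarker interactions, and landmark or joint modelling. It names no validation step either.

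**The concern.** A c-statistic computed in the patients who supplied the coefficients is too high on average. The excess grows with the number of coefficients and shrinks with the number of events. This trial will have few relapses, and the plan speaks of multivariate models without saying how large they will be.

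Two features could turn general optimism into an apparent advantage for sequencing.

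- The 0.58 is not like for like. It describes flow MRD predicting relapse-free survival in other patients, whereas the models here are multivariate and the outcome is relapse.
- Sequencing has more room for choice. Section 2.5.2 describes a 25-gene panel, and Section 10.4.2.1.2 intends to examine specific genes and allele frequencies. Section 10.4.2.1 proposes to use the dataset to learn whether mutations possibly related to clonal hematopoiesis are prognostic, and to re-sequence more deeply the MRD-negative patients who relapsed. No counterpart is described for flow.

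Sections 2.5.2.2 and 10.4.2.1.2 say that a favourable result could support ctDNA-based MRD as a surrogate marker in future trials. An inflated c-statistic would therefore be carried forward.

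**Working it through.** **1. The plan's own figures.** The section gives "a minimum total sample size of 16, 24, 20, and 18 evaluable patients with CR/CRi" for 80% power at one-sided 10%. The first two figures belong to the regimens in this trial and the last two to Aza + Ven arms that it does not have. No hazard ratio or event fraction is given, so the figures can only be solved backwards. Take the stated MRD-negativity ratio r as the allocation, p = r/(1 + r), and Schoenfeld's formula d = (1.2816 + 0.8416)² / [p(1 − p)(ln HR)²], whose numerator is 4.508.

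- r = 1, all 16 with an event: (ln HR)² = 4.508/(0.25 × 16) = 1.127, HR = 2.89.
- r = 3, all 24 with an event: (ln HR)² = 4.508/(0.1875 × 24) = 1.002, HR = 2.72.
- With 50% events the two hazard ratios become 4.5 and 4.1.

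None of this bears on a difference between c-statistics. The plan has no precision figure for that comparison.

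**2. Size of the risk set (assumed).** Section 10.1 plans 50 patients. Section 2.3.1.2 gives 70-80% CR for younger adults; applying that here is an assumption. 50 × 0.70 = 35 and 50 × 0.80 = 40. The relapse fraction is not stated; I used 30-60%. At n = 35-38 this gives 35 × 0.30 = 10.5 to 38 × 0.60 = 22.8 relapses.

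**3. Number of covariates (assumed).** MRD plus the three stratification factors of Section 10.3 makes four coefficients, or 10.5/4 = 2.6 to 22.8/4 = 5.7 relapses per coefficient. I ran 1 to 6.

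**4. Apparent c when nothing predicts.** Cox models were fitted to simulated data with uninformative binary covariates (1,000 runs per setting, n = 35 and 38, 30-60% relapse). Harrell's c = (concordant pairs + ½ tied pairs) / usable pairs was scored in the fitting patients and in new patients.

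| Uninformative covariates | Mean apparent c | Runs above 0.58 | Mean c, new patients |
|---|---|---|---|
| 1 | 0.54-0.57 | 16-34% | 0.50 |
| 2 | 0.57-0.61 | 39-67% | 0.50 |
| 3 | 0.60-0.65 | 60-83% | 0.50 |
| 4 | 0.62-0.68 | 79-95% | 0.50 |
| 6 | 0.65-0.72 | 94-99% | 0.50 |

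At n = 40 with 40-60% relapse, three covariates average 0.595-0.618. Apparent c reaches 0.85 in at most about 4% of runs at n = 35-38 (six covariates, 30% relapse).

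**5. A marker no better than the cited flow result.** Take a binary marker with true c of about 0.58 (hazard ratio 1.9, n = 36, 45% relapse).

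- Alone: apparent c 0.587, new patients 0.565.
- With two uninformative covariates: 0.639 and 0.549.
- With four: 0.681 and 0.545.

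Read against 0.58, the last model shows a gain of 0.681 − 0.58 = 0.10 although the marker is no better.

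**6. When the bias has a direction.** Take n = 38, 45% or 60% relapse, three uninformative covariates and one uninformative marker per method (300 runs each). With one sequencing marker the mean difference in apparent c from flow is about 0. With the best of five candidates, sequencing leads by about 0.03 and wins in 75-79% of runs. With the best of ten it leads by about 0.04 and wins in 83-85%. The exact figures depend on how the winner is picked; the direction does not.

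**The case against.** The strongest reply is that the plan does not say what a reader might infer from it. Section 10.4.2.1.2 does not state that the methods will be compared formally by c-statistic, that c will be scored in the fitting patients, or that 0.58 is the benchmark. The Cox models are described as assessing association, and Section 2.5.2.1 uses the same 0.58 as background. This stands: same-patient scoring and the role of c are inferences from what is left open.

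A flow model in this trial is planned, and with the same number of coefficients it would carry the same optimism. This also stands, and step 6 confirms it for a single marker per method. The inference that the comparison favours sequencing whatever its merit is not supported. Nor is the inference that noise alone beats 0.58 in general: one covariate usually does not, and two are borderline. The hypothesised 0.85 is rarely reached by chance at this sample size.

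Some safeguards exist. Section 10.4.2.1.1 compares DS and flow by a paired McNemar test with researchers blinded to flow results, and Part 2 allows landmark analysis. But McNemar's test compares MRD classifications, not prediction of relapse. Blinding to flow does not prevent tuning on relapse, and the blinding to patient information in Section 10.4.2.1 is described as initial only. Re-sequencing MRD-negative patients who relapsed requires knowing the outcome.

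Finally, the endpoint is exploratory, is called proof of principle, and drives no treatment decision. That limits the weight of the point but does not answer it.

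**Conclusion.** The point holds in a conditional form. With about 35-40 remissions and an unspecified number of covariates, an uncorrected multivariable c-statistic cannot be interpreted. If it is scored in the fitting patients, three or more uninformative covariates average about 0.59-0.72, against 0.50 in new patients. The size rests on the assumed CR rate, relapse fraction and covariate count, none of which the section gives.

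The optimism is not one-sided in itself. It favours sequencing in two circumstances: if the results are read against the external 0.58, or if sequencing markers or thresholds are selected or re-read using the same relapses. The plan leaves both open. The primary endpoint and the secondary analyses are not affected.

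**What to change.** Add to Section 10.4.2.1.2:

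- Fit the flow, DS and cfDNA models in the same patients from the same landmark. The sample after consolidation cycle 1 is one option, since Section 5.1 collects all three specimens then. If serial values are used, use the same schedule for each method.
- Name one small covariate set and change only the MRD term. State the expected number of relapses.
- Define MRD positivity for each method in advance, including the handling of mutations possibly related to clonal hematopoiesis. Keep results from outcome-triggered deeper sequencing out of this comparison.
- Report bootstrap optimism-corrected c-statistics, with any gene, threshold or marker selection repeated inside each bootstrap sample.
- Report the paired difference in corrected c from this trial's flow model, with a confidence interval. Report each method alone as well.
- Cite 0.58 as context only, noting that it refers to relapse-free survival in other patients.

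The cost is analysis wording and a bootstrap, with no new data. The c-statistics will be lower, the difference will be imprecise, and requiring all three methods in the same patients may reduce the number analysed.

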Another small study identified PD-L1 to be preferentially expressed in AML-M5 and at higher surface levels during relapse compared to that at first diagnosis in patients (Chen *et al.*, 2008). Norde *et al* found that in patients who relapsed late after allogeneic transplant, despite the presence of circulating alloreactive T-cells to hematopoietic cell-restricted minor histocompatibility antigens, PD-L1 was highly expressed on the leukemic cells at baseline or upon stimulation with IFN- γ (Norde *et al.*, 2011). Furthermore, stimulation of allogeneic CD3⁺ T-cells with the PD-L1-expressing AML cells led to significantly enhanced T-cell proliferation and cytokine production when performed in presence of anti-PD-1 antibody compared to isotype controls.

Based on these studies, one can speculate that PD-L1 expression is unlikely to be an oncogene-driven tumor immune escape mechanism but rather the result of an initially effective immune response against AML, which is later hampered by IFN-induced upregulation of PD-L1 interacting with PD-1-expressing immune cells (Kronig *et al.*, 2014). As a form of adaptive resistance to therapy, AML cells co-opt the natural physiology of the PD-1/PD-L1 pathway for tissue protection in the face of inflammation, to protect itself from an anti-leukemia response.

A phase 1 trial using CT-011, a humanized antibody blocking with PD-1, in patients with advanced hematologic malignancies (AML, multiple myeloma (MM), Hodgkin lymphoma, and NHL) showed only limited activity (Berger *et al.*, 2008). In a phase 2 trial, nivolumab has been combined with cytarabine and idarubicin for the treatment of 32 AML patients in the frontline setting (Ravandi *et al.*, 2017). Treatment included 1 or 2 induction cycles of cytarabine 1.5 g/m² over 24 hours (Days 1-4) and idarubicin 12 mg/m² (Days 1-3). Nivolumab 3 mg/kg was started on Day 24 ± 2 days and was continued every 2 weeks for up to a year. Of the 32 patients, 23 patients (72%) achieved CR/CRi (19 CR, 4 CRi) and 9 patients went on to receive an allogeneic stem cell transplant (alloSCT). Among the patients proceeding to alloSCT the risk of graft versus host disease (GVHD) was not significantly increased. At baseline, bone marrow of non-responders had significantly higher percentage of CD4⁺ T-effector cells co-expressing the inhibitory markers PD-1 and TIM3 (p<0.05) and a trend towards a higher percentage of CD4⁺ T-effector cells co-expressing PD-1 and LAG3 compared to responders.

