10.2 Sample Size/Accrual Rate

A total of 50 patients (25 per arm) are planned to be enrolled in the intent-to-treat analysis, which will evaluate a 25% difference in the rate of MRD-negative CR/CRi with ~71% power and an overall, one-sided alpha level of 0.1. All patients being randomized and starting induction therapy should be included in the primary analysis.

PLANNED ENROLLMENT REPORT

Racial Categories	Ethnic Categories				Total
	Not Hispanic or Latino		Hispanic or Latino		
	Female	Male	Female	Male	
American Indian/ Alaska Native	0	0	0	0	0
Asian	1	1	0	0	2
Native Hawaiian or Other Pacific Islander	1	1	0	0	2
Black or African American	1	1	1	1	4
White	15	20	1	2	38
More Than One Race	1	1	1	1	4
Total	19	24	3	4	50

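### The 80% power stated for the exploratory cfDNA analysis is unsupported, because it rests on arms and patient numbers that this trial does not have

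*Combined protocol and SAP*

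**What the plan says.** Section 10.4.2.1.2 compares cfDNA-based MRD with duplex sequencing (DS) and flow cytometry (MFC) for predicting relapse, using Cox regression. Its sizing sentence begins "Assuming MRD-negativity (among CR/CRi) ratios of 1, 3, 0.3, and 0.45" and assigns these ratios "for intensive chemo, intensive chemo + Pem, Aza + Ven, and Aza + Ven + Pem arms, respectively". It adds a correlation of 0.75 between the MFC and DS assays and concludes that "a minimum total sample size of 16, 24, 20, and 18 evaluable patients with CR/CRi would provide 80% power", at a "one-sided type-I error of 10% without correction for the multiplicity of endpoints: TTR; DFS; and OS".

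The calculation comes with no hazard ratio, event fraction or follow-up time. The only effect size nearby is a hoped-for c-statistic of 0.85, against 0.58 for MFC in an earlier trial, and it is not converted into a hazard ratio.

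The design is described differently elsewhere. Section 7.1.1 randomises 1:1 to 7+3 alone or 7+3 plus pembrolizumab. Section 10.2 gives the size: "A total of 50 patients (25 per arm) are planned to be enrolled in the intent-to-treat analysis". Part 3 of the biomarker analysis at the end of Section 10.4.2 compares only the two intensive-chemotherapy arms.

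**The concern.** A power figure should describe the trial in which it appears. This one names two treatment groups that are absent from the treatment plan and asks for more responders than there are randomised patients. In one of the two real arms it needs almost every patient to respond. Section 13.2.8 also contains a stray remark about patients after azacitidine-venetoclax. That suggests text carried over from a different design, though the documents do not say so.

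The same section presents ctDNA-based MRD as a possible surrogate marker for future trials. A result from this analysis, positive or null, could therefore be weighed against a stated 80% that was not worked out for this trial.

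**Working it through.** **Inputs**
- Numbers 16, 24, 20 and 18; ratios 1, 3, 0.3 and 0.45; one-sided alpha 0.10; power 80% (Section 10.4.2.1.2).
- 25 patients per arm, two arms, 50 in total (Sections 10.1 and 10.2).
- CR or CR/CRi rates in the background: 23 of 32 (72%) in a frontline trial of intensive chemotherapy plus nivolumab (Section 2.1.2.2.2); 70-80% CR in younger adults on 7+3 (Section 2.3.1.2); 35-50% CR in older or adverse-karyotype patients (Section 2.1.1.1). Eligibility runs to age 75 (Section 3.1.2).

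**Step 1: can the 80% be reproduced?** No. Under Schoenfeld's formula, n × f × p(1−p) × (ln HR)² = (1.2816 + 0.8416)² = 4.508. Here n is the number of CR/CRi patients, f the fraction with an event and p the MRD-negative share. Neither f nor HR is stated. Reading each ratio r as MRD-negative to MRD-positive (assumption), p = r/(1+r):

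| Arm | n | p | n·p(1−p) | HR if f = 1 | HR if f = 0.5 |
|---|---|---|---|---|---|
| Intensive chemo | 16 | 0.50 | 4.00 | 2.89 | 4.49 |
| Intensive chemo + Pem | 24 | 0.75 | 4.50 | 2.72 | 4.12 |
| Aza + Ven | 20 | 0.231 | 3.55 | 3.09 | 4.92 |
| Aza + Ven + Pem | 18 | 0.310 | 3.85 | 2.95 | 4.62 |

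Many pairs of HR and f fit each row. With one common HR and f, the fourth column would be constant apart from rounding; it runs from 3.55 to 4.50. Rounding n up cannot close that gap: n = 16 needs a constant above 15 × 0.25 = 3.75 and at most 4.00, while n = 24 needs one above 23 × 0.1875 = 4.31. The role of the 0.75 correlation is not explained.

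**Step 2: does the total fit?** 16 + 24 + 20 + 18 = 78, against 50 randomised. The absent arms account for 20 + 18 = 38 of the 78.

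**Step 3: are the two real arms' numbers attainable?** The control arm needs 16/25 = 64% in CR/CRi and the pembrolizumab arm 24/25 = 96%. Binomial tails for 25 patients:

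| CR/CRi rate | Expected count | P(≥16) | P(≥24) |
|---|---|---|---|
| 70% | 17.5 | 0.81 | 0.002 |
| 72% | 18 | 0.87 | 0.003 |
| 75% | 18.75 | 0.93 | 0.007 |
| 80% | 20 | 0.98 | 0.03 |
| 90% | 22.5 | >0.99 | 0.27 |

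These count CR/CRi only. Any such patient without a usable sample makes the target harder to reach.

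**Step 4: power at realistic counts, effect and event fraction unchanged.** If n patients give 80% power, m patients give Φ(√(m/n) × 2.1232 − 1.2816). HR, p and f cancel, so no value need be assumed for them.
- Pembrolizumab arm, n = 24, m = 18: 0.8660 × 2.1232 − 1.2816 = 0.557, power 71%.
- Pembrolizumab arm, m = 20: 0.9129 × 2.1232 − 1.2816 = 0.657, power 74%.
- Control arm, n = 16, m = 18: 1.0607 × 2.1232 − 1.2816 = 0.970, power 83%. With m = 20, 86%.

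**Step 5: a between-arm reading.** The sentence speaks of a between-arm difference. If 16 and 24 are the two sides of one comparison, 40 of 50 patients (80%) must reach CR/CRi. The probability is 0.08 at a 70% rate, 0.13 at 72% and 0.58 at 80%.

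**Step 6: primary endpoint.** For 50% versus 75%, 25 per arm and one-sided 0.10, the pooled SE is √(2 × 0.625 × 0.375/25) = 0.1369 and the unpooled SE is 0.1323. Then (0.25 − 1.2816 × 0.1369)/0.1323 = 0.563, power 71.3%, which agrees with the stated figure of about 71%.

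**The case against.** The strongest defence is that little depends on this sentence. The analysis is labelled exploratory, the text openly disclaims any multiplicity correction, no decision rule uses the result, and primary power is sound. Nor do the documents say that a null result would be taken as absence of association. All of this stands and limits the weight of the point.

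The control-arm number is within reach, so the mismatch does not affect both real arms equally. This also stands.

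The 72% rate comes from a different regimen. Section 10.1 expects 75% MRD-negative CR/CRi in the intervention arm which, taken over all randomised patients, implies a CR/CRi rate of at least 75%. That is fair, but the chance of 24 or more is still only 0.007 at 75% and 0.03 at 80%.

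A reader might infer more: that the numbers work only if every CR/CRi patient has an event and that, with realistic censoring, true power is about one half. The documents do not support this. They state no event fraction, and a larger hazard ratio with fewer events fits equally well (about 4.1 to 4.5 at 50% events in the two real arms). Taking a hazard ratio solved with all patients as events and then applying it with far fewer events mixes two assumptions. With one event fraction throughout, the pembrolizumab arm comes to about 71% with 18 patients.

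**Conclusion.** The power statement is wrong as written for this trial. Two of its four arms do not exist here, its 78 CR/CRi patients exceed the 50 randomised, and its pembrolizumab-arm number has a probability of about 0.003-0.03 at CR/CRi rates of 72-80%. Those findings need no assumption beyond the CR/CRi rate.

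The 80% is therefore unsupported. A reader might go on to call it false, but without a hazard ratio or event fraction that cannot be shown. The shortfall to about 71-74% in the pembrolizumab arm rests on two assumptions: that the ratios are MRD-negative to MRD-positive, and that the numbers are per arm. It also takes 18-20 CR/CRi patients in place of 24; at a 60% rate (15 patients) it would be 65%. On the same footing the control arm keeps 83-86% with 18-20 patients and about 78% with 15. The consequence is confined to an exploratory analysis. It should be corrected but does not threaten the trial's main conclusion.

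**What to change.** In Section 10.4.2.1.2, delete the two azacitidine-venetoclax arms with their ratios and numbers, and delete the 80% claim. Then choose one of two courses:

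- Restate power for the two actual arms. Give the hazard ratio, the assumed event fraction and follow-up, the expected number of evaluable CR/CRi patients (about 16-20 per arm, that is 64-80% of 25), and how the 0.75 correlation enters. Say whether the comparison is within each arm by MRD status or between arms.
- Call the analysis descriptive, report estimates with confidence intervals, and make no power claim.

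The cost is a text change only. Accrual, sampling, treatment and the primary analysis are untouched. A restated power for the pembrolizumab arm is likely to look less favourable than 80%.
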